5.7.1. Analysis of Primary Efficacy Variable

The primary analysis is to evaluate the efficacy of REGN9933 for the prevention of VTE after unilateral TKA, compared to enoxaparin. The primary efficacy variable is a binary indicator whether a participant has an adjudicated, confirmed VTE through day 12.

For any participant i , let p_i denote the VTE probability, trt_i denote the treatment assignment (0: enoxaparin, 1: REGN9933, 2: apixaban), $country_i$ denote the country indicator (1, 2, .., K), and age_grp_i be the age group indicator (0: $age < 70$ and 1: $age \geq 70$).

The following Bayesian logistic regression model adjusted by stratification factors (country and age group) is specified to compare the event rates of VTE among enoxaparin, REGN9933, and apixaban:

$$logit(p_i) = \beta_0 + \beta_1 * I(trt_i = 1) + \beta_2 * I(trt_i = 2) + \sum_{k=1}^{K-1} \theta_k * I(country_i = k) + \gamma * age_grp_i$$

where β_0 is the log odds of the VTE rate from enoxaparin, β_1 is the log odds ratio of REGN9933 relative to enoxaparin, and β_2 is the log odds ratio of apixaban relative to enoxaparin after adjustment by country and age group. The benefit of the treatment effect of REGN9933 over enoxaparin is expressed in terms of the odds ratio ($=e^{\beta_1}$) that is less than 1.

A weak prior $N(0,0.843)$ is chosen for parameters β_1 and β_2 . With this weak prior, the extreme treatment difference is unlikely, i.e., the probability of the odd ratio between 0.25 and 4 is around 90%. A vague prior $N(0,10^4)$ is used for the other regression parameters.

The treatment effect will be estimated using the Markov Chain Monte Carlo (MCMC) method via PROC BGLIMM in SAS. The SAS code for implementing the Bayesian logistic regression model is provided in Appendix [11.4.1](#)

Bayesian summary statistics (posterior mean and median, and two-sided 90% credible interval) of the treatment effect of REGN9933 vs enoxaparin (odds ratio = e^{β_1}) will be reported.

Based on the logistic regression model, the treatment effect (odds ratio = $e^{\beta_1 - \beta_2}$) of REGN9933 vs apixaban and the treatment effect (odds ratio = e^{β_2}) of apixaban vs enoxaparin will be reported. Their credible interval such as two sided 90% credible interval will also be reported.

The probability-based quantities for the magnitude of treatment effect at thresholds of clinical interest may be provided, e.g., $Prob(OR < 0.5, 0.8, 0.9, \text{etc.} | \text{data})$.

5.7.2. Analysis of Secondary and Exploratory Efficacy Variables

Unless otherwise specified, categorical efficacy endpoints (defined in Section [4.4.2](#) and Section [4.4.3](#)) will be analyzed by Bayesian logistic regression models in a similar manner for the primary efficacy variable on the mITT set.

Bayesian summary statistics (posterior mean and median, and two-sided 90% credible interval) of the treatment effect (odds ratio) will be reported.

For the exploratory analyses, the distribution of DVT (proximal versus distal) will be summarized descriptively for participants detected on venogram. Proximal DVT will be characterized by the size of the venous thromboembolism (VTE), while distal DVT will be summarized by the number of affected veins.

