8.3.2. Study Intervention Discontinuation

Participants who permanently discontinue from study intervention (REGN9933, enoxaparin, or apixaban) should be encouraged to remain in the study. Those who agree and do not withdraw from the study will be asked to return to the clinic for all remaining study visits per the visit schedule.

Participants who permanently discontinue from study intervention and who opt to withdraw from the study will be asked to complete study assessments, per Section 9.1.2.

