3.1. Efficacy Analysis Set

The primary analysis will be conducted in the modified intention to treat population (mITT) population, consisting of randomized and treated participants that have either an evaluable venogram, a confirmed episode of venous thromboembolism, or both through day 12. It is based on the treatment allocated (as randomized).

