4.4.3. Exploratory Efficacy Variables

- Incidence of confirmed VTE through day 12 (REGN9933 vs apixaban) and through the end of study
- Incidence of major VTE through the end of study

- Incidence of confirmed symptomatic DVT in either leg through day 12 or through the end of the study
- Incidence of confirmed PE through day 12 and through the end of study
- Incidence of fatal PE, which includes sudden death for which PE cannot be ruled out, through day 12 and through the end of study
- Incidence of DVT as measured by venography of the operated leg on day 10 ± 2 days (REGN9933 vs apixaban)
- In participants with DVT detected on venogram:
 - distribution of DVT (proximal versus distal)
 - for proximal DVT, size of VTE
 - for distal DVT, the number of veins affected

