5.7. Analysis of Efficacy Variables

The efficacy analyses will be performed using the mITT analysis set.

Pooling of Sites/Centers

For this multi-center study, a small number of participants are anticipated at some sites. Since these study sites may not provide appropriate information to allow the analysis, the efficacy analyses adjusted/stratified by country instead of site will be conducted.

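### Symptomatic DVT, PE and fatal PE are analysed on the venogram-dependent mITT, which overstates their incidence and treats late events inconsistently

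*SAP*

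**What the plan says.** - **Analysis set.** SAP 5.7 opens with "The efficacy analyses will be performed using the mITT analysis set". SAP 5.7.2 adds that, unless otherwise specified, the categorical endpoints of 4.4.2 and 4.4.3 "will be analyzed by Bayesian logistic regression models in a similar manner for the primary efficacy variable on the mITT set". Nothing else is specified for symptomatic DVT, PE or fatal PE. Table 1 in SAP 11.1 names no other set for efficacy, and the sensitivity analyses in 5.7.3 vary priors, covariates and method but not the population.
- **Who is in it.** SAP 3.1 restricts the mITT to "randomized and treated participants that have either an evaluable venogram, a confirmed episode of venous thromboembolism, or both through day 12". Protocol 11.3.1 defines the mITT without the day-12 limit, while SAP 1.4 declares no change from the protocol.
- **Endpoints.** SAP 4.4.3 words the PE endpoint as "Incidence of confirmed PE through day 12 and through the end of study". It lists symptomatic DVT (either leg) and fatal PE with the same two time points.
- **Follow-up.** Protocol Table 2 schedules assessment for symptomatic VTE at Visits 2 to 6, the last on day 75. Protocol 9.2.2.2 has suspected events confirmed by ultrasound, CT, ventilation/perfusion scan or similar tests. Protocol 8.3.2 says that participants who stop treatment but stay in the study "will be asked to return to the clinic for all remaining study visits per the visit schedule". Protocol 9.2.2.1 foresees non-evaluable venograms but gives no expected rate.

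**The concern.** For a composite that is mostly asymptomatic DVT, leaving out participants without an evaluable venogram is a recognised choice, because their outcome is unknown. For symptomatic DVT, PE and fatal PE the outcome is known without the venogram. Applying the mITT to them makes entry depend on the outcome. Among treated, followed participants without an evaluable venogram:

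| Course | SAP 3.1 mITT | Protocol 11.3.1 mITT |
|---|---|---|
| VTE by day 12 | in, event counted | in, event counted |
| No VTE to day 75 | out | out |
| First VTE on days 13 to 75 | out, event not counted | in, event counted |

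At stake are the incidence estimates for the exploratory objective on symptomatic, clinical thrombosis. The protocol's risk-benefit section cites symptomatic VTE in fewer than 2% of participants in earlier FXI studies, so one event kept or dropped is a visible part of each arm's count.

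**Working it through.** The plan states no figure on this point, so there is none to reproduce. The check is denominator algebra.

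**Inputs.** N = 120 per arm (SAP 2.1). True day-12 symptomatic risk s: 2%, the ceiling of the figure cited in Protocol 3.3.1, with 0.5% as a lower case. Share e of event-free participants with an evaluable venogram: 90% to 70%, assumed.

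**1. Day-12 incidence.** All sN events stay in, and event-free participants stay in only with an evaluable venogram:

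mITT rate = sN / [sN + (1 − s)eN]; inflation = 1 / [s + (1 − s)e].

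For s = 2%, sN = 2.4 and (1 − s)N = 117.6:

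| e | Denominator | mITT rate | Inflation |
|---|---|---|---|
| 0.90 | 2.4 + 105.84 = 108.24 | 2.22% | 1.11 |
| 0.80 | 2.4 + 94.08 = 96.48 | 2.49% | 1.24 |
| 0.70 | 2.4 + 82.32 = 84.72 | 2.83% | 1.42 |

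For s = 0.5% the inflation is 1.11, 1.25 and 1.43, so it hardly depends on s.

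**2. Day-12 odds ratio.** The mITT odds are [s/(1 − s)]/e. The odds ratio of enoxaparin relative to REGN9933 is therefore the true one multiplied by e(REGN9933)/e(enoxaparin).
- Equal e: the factor is 1, so there is no bias.
- 10% vs 15% of event-free participants missing (REGN9933 vs enoxaparin): 0.90/0.85 = 1.06.
- 10% vs 25% missing: 0.90/0.75 = 1.20.
- Reversing the imbalance inverts the factor.

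These are raw ratios. The planned model puts a N(0, 0.843) prior on the log odds ratio. In the 1.20 case the log-OR variance is 1/2.4 + 1/2.4 + 1/105.84 + 1/88.2 = 0.854. Reading 0.843 as the SD, the prior variance is 0.711 and the weight on the data is 0.711/(0.711 + 0.854) = 0.454. The estimate shrinks to exp(0.454 × 0.182), about 1.09, with a 90% interval of roughly 0.39 to 3.0 (normal approximation). The 1.06 case shrinks to about 1.03.

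**3. End of study.** Assume a late risk of 0.5% to 1% (0.6 to 1.2 events per arm on days 13 to 75), unrelated to evaluability. Under SAP 3.1 a share 1 − e of late events leaves the model: from 0.10 × 0.6 = 0.06 to 0.30 × 1.2 = 0.36 per arm, or about 0.2 to 1.1 over three arms.

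The two definitions then give different rates. Take 1% risk by day 12, 1% late and e = 0.80, so the true end-of-study rate is 2%:
- SAP 3.1: (1.2 + 0.96) / (1.2 + 118.8 × 0.80) = 2.16/96.24 = 2.24%.
- Protocol 11.3.1: 2.4 / (2.4 + 117.6 × 0.80) = 2.4/96.48 = 2.49%.

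Even where the SAP set loses late events, the rate is still too high on balance, because the denominator shrinks more.

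**4. On all dosed participants, as randomised.** The denominator is 120 and the rate is s. For example, take 24 of 120 without an evaluable venogram and two symptomatic events by day 12, one of them among those 24. The rate is 2/120 = 1.67%, against 2/(96 + 1) = 2.06% on the mITT, a ratio of 1.24.

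**The case against.** The strongest reply is that little hangs on this. Taken singly, these endpoints are exploratory. The reported treatment effect is an odds ratio, which is unbiased at day 12 when evaluability is equal across arms. With two or three events per arm, uncertainty swamps any bias. All of that stands and limits the weight of the point. It does not rescue the incidences, which is how these endpoints are worded and which are wrong even with equal missingness.

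Two stronger readings are tempting, and the documents do not support them.
- A reader might infer that the plan discards late PEs and deaths. Only participants with neither an evaluable venogram nor a VTE by day 12 leave the SAP's set; all other late events stay. AEs are collected to end of study, and SAEs, TEAEs leading to death and a summary of deaths are reported on the safety set (SAP 5.8.1). What is missing is those events' place in the between-arm efficacy estimate.
- A reader might infer a spurious treatment effect of the order of 1.20. That needs a 10% vs 25% imbalance. The open-label design makes some imbalance possible, but no document gives a size or a direction for it, and the planned prior would pull 1.20 to about 1.09.

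It may also be said that the protocol's FAS sensitivity analysis covers this. It is described beside the primary analysis, is not assigned to these endpoints, and does not appear in SAP section 3, 5.7.3 or Table 1.

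**Conclusion.** The point holds as a limited one. SAP 3.1, 5.7 and 5.7.2 together put three clinically assessed endpoints on a set whose membership depends partly on those same outcomes. Day-12 incidence is overstated by about 1.1 to 1.4 times for evaluable shares of 90% to 70%. The direction follows from the definitions; the size rests on that assumed range. Bias in the odds ratio is conditional on unequal evaluability and modest in plausible cases (raw 1.06 for 10% vs 15% missing). For end-of-study endpoints the SAP's mITT leaves some late events out of the model and the protocol's mITT counts them without their event-free counterparts. Neither gives the right incidence. The primary analysis is not affected by this point.

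**What to change.** 1. In SAP 5.7.2 and Table 1, analyse symptomatic DVT, PE and fatal PE, through day 12 and through end of study, on all randomised participants who received study drug, as randomised. Protocol 11.3.1 already defines this set as the FAS; add it to SAP section 3.
2. State a rule for participants lost before the time point. The planned binary logistic model cannot censor, so this means either a missing-outcome rule or a time-to-event estimate for these endpoints.
3. Keep the mITT for endpoints that need the venogram.
4. Reconcile the mITT definitions in Protocol 11.3.1 and SAP 3.1, and record the outcome in SAP 1.4.
5. List by arm every adjudicated VTE and death outside the mITT, including those that belong to confirmed and major VTE through end of study, where the same late events can drop out.

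The cost is some SAP text, a population flag, one listing and a decision on early losses. No new data are needed.

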5.7.3. Sensitivity Analysis

To assess the robustness of the Bayesian model on the choice of prior distributions, sensitivity analyses will be performed and reported for these possible prior distributions for parameters β_0 , β_1 , and β_2 (including but not limited: $N(0,1)$, $N(0,10)$, $N(0,100)$, and $N(0,10^6)$).

A Bayesian logistic regression model with these two covariates (country and treatment group) will be explored to assess the treatment effect conditional on country only.

To assess the sensitivity of the Bayesian logistic model, the stratified Cochran-Mantel-Haenszel (CMH) method by both country and age group will be performed. The SAS code for CMH analysis is provided in Appendix 11.4.2. The stratified CMH by country only as the stratification factor will also be explored.

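### Every prior named for the SAP 5.7.3 sensitivity runs is wider than the primary prior on the treatment effect, so the set cannot show whether a favourable result survives more scepticism; N(0,1) on the intercept adds a separate artefact

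*SAP*

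**What the plan says.** SAP 5.7.1 sets up a three-arm logistic model with enoxaparin as reference. For the two treatment log odds ratios, beta1 (REGN9933) and beta2 (apixaban), "A weak prior $N(0,0.843)$ is chosen for parameters" beta1 and beta2. It explains the choice thus: "With this weak prior, the extreme treatment difference is unlikely", and "the probability of the odd ratio between 0.25 and 4 is around 90" per cent. For everything else, including the intercept and the country and age terms, "A vague prior $N(0,10^4)$ is used for the other regression parameters". The intercept beta0 "is the log odds of the VTE rate from enoxaparin".

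SAP 5.7.3 then addresses robustness to the prior: "sensitivity analyses will be performed and reported for these possible prior distributions for parameters" beta0, beta1 and beta2. The same section plans a model without age and a stratified CMH analysis; these vary the model, not the prior. The named priors form an open list: "including but not limited: $N(0,1)$, $N(0,10)$, $N(0,100)$, and $N(0,10^6".

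**The concern.** A prior-sensitivity analysis should bracket the primary prior, so that the reader sees the result under both more and less scepticism. Here all the named alternatives lie on one side. Each is centred on no effect and each weakens the shrinkage that the primary prior applies. If the data favour REGN9933, the usual consequence is that the primary result is the least favourable figure in the robustness table, and agreement across the table says nothing about a more sceptical reader's answer.

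The intercept raises a second problem. The primary prior on beta0 is vague. The sensitivity list names beta0 alongside the treatment parameters, so N(0,1) would make the enoxaparin log odds informative around zero, that is, around a 50% VTE rate. The plan assumes 22.4%. That run then mixes a change in the treatment prior with a misplaced control-rate prior.

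**Working it through.** **Inputs.** Primary and sensitivity priors: SAP 5.7.1 and 5.7.3. Rates of 13% (REGN9933) and 22.4% (enoxaparin), and 120 per arm: SAP 2.2. Expected events: 0.224 × 120 = 26.9, taken as 27; 0.13 × 120 = 15.6, taken as 16. The documents give no apixaban rate. I assume 20 of 120 and show 16 to 40.

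**1. The plan's own prior statement.** SD = ln 4 / 1.645 = 1.386 / 1.645 = 0.843. With 0.843 as an SD, P(0.25 < OR < 4) = 2Φ(1.386/0.843) − 1 = 0.900, as stated. As a variance, SD = √0.843 = 0.918 and the probability is 0.869. So 0.843 works as an SD. The SAP does not say which convention the sensitivity list follows, and the code in Appendix 11.4.1 reads its priors from a data set that is not shown.

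**2. Width of the named priors.** P(0.25 < OR < 4) falls from 0.900 to 0.834 under N(0,1), and to 0.339 (variance 10) or 0.110 (SD 10) under N(0,10). It is lower still for the other two. All four are wider than the primary under either convention.

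**3. Intercept.** logit(0.224) = ln(0.224/0.776) = −1.24, which is 1.24 SDs below the centre of N(0,1). Every beta0 prior, the primary included, has mean zero. Only N(0,1) is narrow enough to matter.

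**4. Posterior.** The posterior is proportional to the three binomial likelihoods times the priors, with logit p = beta0 (enoxaparin), beta0 + beta1 (REGN9933) and beta0 + beta2 (apixaban), integrated on a grid. Events are enoxaparin/REGN9933/apixaban of 120.

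| Prior run | 27/16/20: Pr(OR_RE<1) | 27/16/20: median OR | 25/16/20: Pr(OR_RE<1) |
|---|---|---|---|
| Primary | 0.955 | 0.59 | 0.922 |
| N(0,1) on beta1, beta2; beta0 vague | 0.960 | 0.57 | 0.927 |
| N(0,1) on all three | 0.974 | 0.54 | 0.952 |
| N(0,10) on all three | 0.970 | 0.53 | 0.941–0.942 |
| N(0,100), N(0,10^6): effectively flat | 0.970 | 0.53 | 0.941 |
| SD 0.42 on beta1, beta2; beta0 vague | 0.915 | 0.70 | 0.876 |

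The SD of 0.42 is illustrative: ln 2 / 1.645 = 0.421 puts 90% of the prior on OR 0.5 to 2. At 27/16/20 the upper 90% credible limit is about 0.98 under the primary prior and 1.07 under SD 0.42.

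**5. Share due to beta0.** 0.974 − 0.960 = 0.014 at 27/16/20, and 0.952 − 0.927 = 0.025 at 25/16/20. In the second case the N(0,1) run exceeds the flat-prior answer (0.952 against 0.941), which loosening the treatment prior alone does not do.

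**6. Apixaban assumption.** With 27 and 16 events and apixaban at 16, the primary gives 0.951, the named runs 0.970–0.972 and SD 0.42 gives 0.896. With apixaban at 40: 0.969, 0.970–0.980 and 0.966.

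**7. Covariates.** Adding age and 1, 3 or 6 countries at 27/16/20 gives 0.955–0.957 for the primary and 0.973–0.974 for N(0,1) on all three.

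**8. Direction.** I scanned enoxaparin 8–45, REGN9933 3–44 (below enoxaparin) and apixaban 3–55 events. Where apixaban had no more events than enoxaparin, no result with primary Pr(OR_RE<1) above 0.5 fell under N(0,1), N(0,10) or N(0,100). Where apixaban did worse, N(0,10) and N(0,100) could lower it: under N(0,100), 22/20/34 goes from 0.669 to 0.634 and 22/21/40 from 0.626 to 0.567. The reason is that apixaban shares beta0. The primary prior draws the enoxaparin rate towards a higher apixaban rate, and loosening it removes that pull.

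**The case against.** The strongest reply has five parts.

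- **Vaguer priors are a fair comparison.** An informative primary prior should be compared with vaguer ones, and the primary already shrinks towards no effect. This stands. At the design rates the primary is the more conservative figure, and the gap to the flat-prior runs does display some dependence on the prior.
- **The list is open.** This stands in part: a sceptical prior is not excluded. But one added later is not pre-specified, in an open-label trial whose sponsor-run interim may include efficacy data (SAP 7).
- **CMH is also planned.** It uses no prior, so it is free of the beta0 artefact. For the same reason it cannot represent more scepticism.
- **The text does not say that one prior is set on all three parameters in each run.** True. That is the natural reading, and the beta0 point depends on it. The width point does not.
- **SAP 5.7.5 frames inference as estimation.** True, but the estimate moves too: 0.59 to 0.53–0.54, against 0.70 under SD 0.42.

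Three stronger inferences are tempting and not supported. A reader might infer that the named runs can only help REGN9933; the 22/20/34 and 22/21/40 examples refute that. A reader might infer that the runs turn a failed trial into a success because some cross 0.95. But 0.95 appears only in the sample-size reasoning, not as a success rule, and crossings depend on the count: at 27/17/17 the primary gives 0.932 and all four runs exceed 0.95, while at 25/16/20 only N(0,1) does. Finally, N(0,1) does not assert a 50% rate: its central 95% range is about 12% to 88%.

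**Conclusion.** The point holds as a gap in the sensitivity plan, not as a fault in the primary analysis. All four named priors loosen the prior on the treatment effect and none tightens it. At about the design rates they raise Pr(OR_RE<1) by 1.5 to 2 percentage points, whereas a prior with 90% of its mass on OR 0.5 to 2 lowers it by 4 points (0.955 − 0.915). The planned table would show only the first movement. If N(0,1) is also placed on beta0, about 0.015–0.025 of that run's probability comes from the misplaced control-rate prior.

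These sizes rest on 120 evaluable participants per arm, the plan's assumed rates and an assumed apixaban count. They shrink as apixaban does worse: at 40 apixaban events the effectively flat runs and SD 0.42 all lie close to the primary. The choice of SD 0.42 is mine, not the documents'.

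**What to change.** In SAP 5.7.3:

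1. Keep the vague N(0,10^4) prior on beta0, country and age in every run, and vary only the prior on beta1 and beta2.
2. Pre-specify at least one zero-centred prior narrower than the primary, for example log(OR) with SD 0.42 (90% mass for OR 0.5 to 2).
3. State whether the second argument of each prior is an SD or a variance, and give the prior data set that the Appendix 11.4.1 code reads.
4. Report the median OR, credible interval and Pr(OR_RE<1) side by side for the sceptical, primary and flat priors, with the three arms' event counts. If apixaban does worse than enoxaparin, the shared intercept can blunt or reverse the effect of narrowing both contrasts, and the reader needs the counts to see that.

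The cost is a wording change and one extra model run. The downside for the sponsor is a robustness range that includes a less favourable figure.

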5.7.4. Subgroup Efficacy Analysis

Subgroup efficacy analyses on the primary efficacy variable and secondary efficacy variables will be performed on the following subgroups:

- Gender (Male, Female)
- BMI
- Age group(<70 vs ≥ 70)
- Site
- Country
- Duration of TKA surgery

However, as such analyses may not have enough power for hypothesis tests, the analysis will be exploratory in nature.

5.7.5. Multiplicity Control

As the statistical inference for this study is to focus on estimation rather than testing a formal hypothesis and the Bayesian analysis is performed, the multiplicity adjustments of the different comparisons between groups will not be done.

